## **6.4 Discontinuation of Study Intervention and Participant Discontinuation/Withdrawal**

### **6.4.1 Screen Failures**

Screen failures are defined as participants who consent to participate in the clinical study but are not subsequently assigned to study intervention/entered in the study. A minimal set of screen failure information is required to ensure transparent reporting of screen failure participants to meet the Consolidated Standards of Reporting Trials (CONSORT) publishing requirements and to respond to queries from regulatory authorities. Minimal information includes demography, screen failure details, eligibility criteria, and any serious adverse event (SAE).

A participant who, for any reason – e.g., failure to satisfy the selection criteria – terminates the study before the time point used for the definition of “dropout” is regarded a “screening failure”. A participant who discontinues study participation prematurely for any reason is defined as a “dropout” if the participant has already been administered at least one dose of the study medication.

Individuals who do not meet the criteria for participation in this study (screen failure) may/may not be rescreened, with the following exceptions:

- The participant had successfully passed the screening procedures, but could not start subsequent treatment on schedule.
- Initial screening occurred too early to complete the required washout period after prior therapy.
- The inclusion/exclusion criteria preventing the participant’s initial attempt to participate have been changed (via protocol amendment).

In any case, the investigator has to ensure that the repeated screening procedures do not expose the participant to an unjustifiable health risk. Also, for re-screening, the participant has to re-sign the

informed consent form, even if it was not changed after the participant's previous screening. Rescreened participants should be assigned a new participant number.

#### **6.4.2 Participant Discontinuation/Withdrawal from the Study**

- A participant may withdraw from the study at any time at his/her own request, or at the request of their legally acceptable representative, or may be withdrawn at any time at the discretion of the investigator for safety, behavioral, compliance, or administrative reasons.
- A participant may be withdrawn from the study at the specific request of the sponsor and in liaison with the investigator (e.g. obvious non-compliance, safety concerns).
- At the time of discontinuing from the study, if possible, an early discontinuation visit should be conducted, as shown in the Schedule of Activities (SoA). See SoA for data to be collected at the time of study discontinuation and follow-up and for any further evaluations that need to be completed.
- The participant will be permanently discontinued both from the study intervention and from the study at that time.
- If the participant withdraws consent for disclosure of future information, the sponsor may retain and continue to use any data collected before such a withdrawal of consent.

#### **6.4.3 Lost to Follow Up**

A participant will be considered lost to follow-up if he or she repeatedly fails to return for scheduled visits and is unable to be contacted by the study site.

The following actions must be taken if a participant fails to return to the clinic for a required study visit:

- The site must attempt to contact the participant and reschedule the missed visit as soon as possible and counsel the participant on the importance of maintaining the assigned visit schedule and ascertain whether or not the participant wishes to and/or should continue in the study.
- Before a participant is deemed lost to follow up, the investigator or designee must make every effort to regain contact with the participant. These contact attempts should be documented in the participant's medical record.
- Should the participant continue to be unreachable, he/she will be considered lost to follow up.

#### **6.5 Replacement**

Participants who drop out will be replaced by another participant who will qualify on inclusion and exclusion criteria.

#### **6.6 Participant Identification**

Each participant is identified by the study site's unique participant identification (SID) code. After informed consent/assent procedure every participant is given a screening number (SNR). Following assessment of inclusion and exclusion criteria, participants who meet the entry criteria will be sequentially assigned to a three-digit number in ascending order.

At the beginning of screening every participant is given a participant number (9 digit number consisting of: Digits 1 to 2 = Country code (*Code 14 is the U.S. country code*))

Digits 3 to 5 = Center number within the country (*Code 001 for first center, 002 for second center and so on*)

Digits 1 to 5 = Trial unit (*For the first site, the center/trial number is 14001 which consists of the country code and the center number.*)

Digits 6 to 9 = Current patient/Participant number within the center (*Participant numbers are the last four digits of the nine digit participant identification. First participant number at the first center is 160010001; second participant number is 160010002 and so on, which includes the country code, center number, and participant number. Participant numbers and screening numbers are the same number.*)

## 7. TEST PRODUCTS

### Test Products to be Administered/Tested

There is one test product to be administered/tested in this study:

**Table 2:** Test Product

Product (UI Number: 1613932)	Strength	Dosage Form or Quantity	Route of Administration
Loratadine Chewable Tablet	10 mg	1 Chewable Tablet*	Oral
*Each tablet to be chewed completely before swallowing. Participants are not allowed to drink water until the end of the visit			
Excipients (identification of potentially allergenic compounds may have to be considered)			
Anhydrous Citric Acid			
Aspartame			
Colloidal Silicon Dioxide			
FD&C Blue #1 Aluminum Lake			
Flavor, CCI [REDACTED]			
Flavor, CCI [REDACTED]			
Magnesium Stearate			
Mannitol			
Menthol			
Microcrystalline Cellulose			
Sodium Starch Glycolate			
Stearic Acid			

## 7.1 Identity of Test Product

All test products will be labeled according to the requirements of local law and legislation. Label text will be approved according to the sponsor's agreed procedures, and a copy of the labels will be made available to the study site upon request.

All study drugs will be stored at the investigational site in accordance with GCP and GMP requirements and the instructions given by the clinical supplies department of the sponsor (or its affiliate/CRO), and will be inaccessible to unauthorized personnel. Special storage conditions and a complete record of batch numbers and expiry dates can be found in the Sponsor's study file; the site-relevant elements of this information will be available in the investigator site file. On the day of receipt, the responsible site personnel will confirm receipt of study investigational products in writing. The personnel will use the study investigational products only within the framework of this clinical study and in accordance with this protocol. Receipt, distribution, return and destruction (if any) of the study drug must be properly documented according to the sponsor's agreed and specified procedures.

## 7.2 Test Product Assignment

The sample will be evaluated in a single monadic way (single product is rated by respondents), in a non-randomized fashion. The test produce to be evaluated will be blinded to the participants but not the site staff.

## 7.3 Administration

Regarding amount, route / mode of administration, formulation(s) and duration of testing, refer to [Section 7](#)

Each qualified participant will assess one (1) chewable tablet during each of his/her visit. Each participant will be at the site for approximately 60-75 minutes.

## 7.4 Blinding

As this is a single monadic study, the study will be performed in an open label design because the site technician will dispense the chewable tablets in dosing cups and then provide to test participants. The participants will have a chance to visually inspect the product prior to administration and will be blinded to brand.

## 7.5 Test Product Logistics and Accountability

All test products will be stored at the investigational site as per labeling requirements and the instructions given by the trial supplies department of the sponsor (or its affiliate/CRO), and will be inaccessible to unauthorized personnel. On the day of receipt, the responsible site personnel will confirm receipt of test product in writing. The personnel will use the test product only within the framework of this study and in accordance with this protocol. Receipt, distribution, return and destruction (if any) of the test product must be properly documented according to the sponsor's agreed and specified procedures.

## **7.6 Test Product Compliance**

A member of the investigator's team will monitor the administration of the study product. This person(s) will ascertain and document that the participant receives the test product as planned.

## **8. NON-STUDY THERAPY**

At the screening, potential participants will be asked questions from the health eligibility case report form (CRF) that verifies each participant meets the inclusion/exclusion criteria and qualifies for the study.

Any medication or vaccine (including over-the-counter or prescription medicines, vitamins, and/or herbal supplements) that the participant is receiving at the time of enrollment or receives during the study must be recorded along with:

- Reason for use
- Dates of administration including start and end dates
- Dosage information including dose and frequency

Participants should not use antihistamine products 24 hours before and after the treatment

## 9. PROCEDURES AND VARIABLES

### 9.1 Tabular Schedule of Evaluations

	Pre- Study (-30 Day to -1 Day)	Visit 1 (Day 1)										
		Baseline	10 s.	30 s.	1 min.	(4 min interval)	5 min.	10 min.	15 min.	... *	60 min.	End of Study and Follow- up
Pre-Screening	X											
Informed Consent		X										
Medical/Medicat ion History		X										
Demographics		X										
Verification of Inclusion & Exclusion Criteria		X										
Allergy Profile Questionnaire		X										
Test Product Administration		X										
Cooling Time Point Assessment			X	X	X		X	X	X	X	X	
Sensory Attributes Questionnaire						X						
Open Ended Questions												X
Adverse Event Monitoring		X	X	X	X	X	X	X	X	X	X	X †

(...)\* Time points are at 5-minute intervals up to the last time point.

†At the End of Study, if a participant has an ongoing adverse event, the adverse event will be monitored and recorded and the participant will be contacted during the following week after discharge from the study site.

s= seconds, min= minutes

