#### **Visit 1 (Day 1)**

- One test product will be provided in a dosing cup to each participant who will then be asked to completely chew completely before swallowing. Participants cannot drink water until end of visit.
- Study staff initiates timer as soon as the study medication is administered
- Participant will be asked to indicate on the case report form (CRF) if he/she perceives a cooling sensation in the mouth, nose and throat at 10 seconds, 30 seconds and 1 minutes post ingestion of test product
- After the 1-minute time point, participants will be asked to complete a brief questionnaire on the sensory attributes of the test product. Participants will be allowed four (4) minutes to complete the questionnaire.
- Following the completion of the questionnaire, participants will continue to evaluate perception of cooling sensation in the mouth, nose and throat at 5 minute intervals, starting at the 5 minute time point for 60 minutes
- Following completion of all study assessments, participants will be asked open ended questions which will be used for learning purposes
- Adverse events, if applicable, will be recorded
- Participants will be reminded to report any unusual or unexpected medical changes within the 24 hour period following administration of the study medication to site personnel

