**9.4.2 Sensory Attributes Questionnaire**

Participants will be instructed to complete the questionnaire as following:

“Please indicate to what level you agree or disagree with the corresponding statement:”

Question	Strongly agree (5)	Somewhat agree (4)	Neither agree nor disagree (3)	Somewhat disagree (2)	Strongly disagree (1)
The product provides a cooling sensation					
The product provides a cooling sensation in the mouth					
The product provides a cooling sensation in the nose					
The product provides a cooling sensation in the throat					
The product provides a refreshing sensation					
The product provides a refreshing sensation in the mouth					
The product provides a refreshing sensation in the nose					
The product provides a refreshing sensation in the throat					
The product tastes great					
The product experience was enjoyable					

I like the flavor sensation of the product					
The product feels soothing on the throat					
The sensory experience is unique for an allergy medicine					
The cooling sensation is refreshing					

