#### **Statistical and Analytical Plans**

**Questionnaire:** The primary variable of interest will be analyzed by determining the percentage of selection of the top 2 choices (strongly agree and somewhat agree). This percentage and its 95% confidence interval will be calculated, if the lower bound of the confidence interval is greater than 50%, the statistical majority of agreement will be claimed. Other secondary variables of interests from the questionnaire will be analyzed in the same manner as the primary variable.

**Time to perception of cooling and duration of cooling:** These secondary variables will be analyzed descriptively (Mean, Standard deviation, Median, Mode and Range). The mean time point at which cooling is initially perceived will be claimed as the onset of cooling. The mean time point at which cooling is perceived to last will be claimed as the duration of cooling.

Participants who never reach “Yes” in the perception of cooling will be (1) imputed by the maximum study time (60 minutes), and (2) treated as censored and used Kaplan-Meyer to estimate the median time to perception of cooling.

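### Onset is claimed as a mean of scheduled reading times, which records onsets late; the readings support only an interval or a statement of the form 'by the X reading'

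*Combined protocol and SAP*

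**What the plan says.** Section 9.2.4 (Visit 1) has participants report cooling in mouth, nose and throat "at 10 seconds, 30 seconds and 1 minutes post ingestion of test product". The sensory questionnaire follows: "Participants will be allowed four (4) minutes to complete the questionnaire". Cooling readings then resume "at 5 minute intervals, starting at the 5 minute time point for 60 minutes". The form in Section 9.4.1 lists the same 15 readings. The Section 9.1 schedule marks no cooling assessment in the column labelled "4 min interval".

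The questionnaire in Section 9.4.2 does ask about cooling, for example "The product provides a cooling sensation in the mouth". It asks for agreement and not for a time, so it cannot date an onset.

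Section 10.3, like the Synopsis, states: "The mean time point at which cooling is initially perceived will be claimed as the onset of cooling". Median, mode, standard deviation and range are also to be reported. Participants who never perceive cooling are handled in two ways: they are given 60 minutes, and they are "treated as censored and used Kaplan-Meyer to estimate the median time to perception of cooling". Neither section treats an onset as lying between two readings.

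**The concern.** The time at which cooling is first recorded is the right-hand end of the interval in which it began. Averaging those right-hand ends gives a figure that depends on the spacing of the readings as well as on the product. Participants whose cooling starts at 61 s and at 299 s both enter the mean as 300 s.

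What is at stake is the accuracy of a number that the plan commits to claiming. The same tablet read on a different grid would yield a different claimed onset.

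**Working it through.** **Inputs from the documents.** Reading times g = 10 s, 30 s, 1 min, 5 min, 10 min, …, 60 min (Sections 9.1, 9.2.4 and 9.4.1). The claimed figure is the mean of the first reading with cooling (Section 10.3). The plan states no expected onset, so there is no figure of its own to reproduce.

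**Assumption.** The documents give no distribution F of true onset times. I used exponential and lognormal shapes over a range. Participants who never perceive cooling are left out at this stage, to isolate the effect of the grid.

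**Formula.** Recorded mean = Σ g_j × [F(g_j) − F(g_(j−1))] / F(60 min). It is compared with the true mean among those with onset by 60 min.

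**Example 1: exponential, true mean 1 min.** The shares first recorded at 10 s, 30 s, 1, 5 and 10 min are 0.1535, 0.2400, 0.2387, 0.3611 and 0.0067.

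0.1535 × 0.167 + 0.2400 × 0.5 + 0.2387 × 1 + 0.3611 × 5 + 0.0067 × 10 = 0.026 + 0.120 + 0.239 + 1.806 + 0.067 = 2.26 min, or 2.26 times the true mean.

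**Example 2: lognormal, median 20 s, log-SD 1.0.** The true mean is 20 × exp(0.5) = 33 s. The recorded mean is 69 s, a ratio of 2.1 and an error of 36 s. About 13% of onsets fall between 1 and 5 min, and they account for about 72% of the excess. By the 1-minute reading 86% have already perceived cooling, yet the claimed onset would be 69 s.

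**Range for exponential onsets**

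| True mean (min) | Recorded mean (min) | Ratio |
|---|---|---|
| 0.25 | 0.48 | 1.9 |
| 0.5 | 1.13 | 2.3 |
| 1.0 | 2.26 | 2.3 |
| 1.5 | 3.06 | 2.0 |
| 2.0 | 3.74 | 1.9 |
| 3.0 | 4.94 | 1.6 |
| 5.0 | 7.13 | 1.4 |
| 9.85 | 12.15 | 1.2 |

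The lognormal results depend on spread. Medians of 10 to 30 s with log-SD 0.8 to 1.2 give about 1.9 to 2.2. A median of 20 s with log-SD 0.3 gives 1.55 (21 s recorded as 33 s, rounded). A median of 1.25 min with log-SD 0.3 gives 3.1.

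**How much is due to the 1–5 min gap?** I added hypothetical readings at 2, 3 and 4 min, purely as a diagnostic.

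| Assumed onset | Ratio, actual grid | Ratio, gap filled |
|---|---|---|
| Exponential, mean 1 min | 2.26 | 1.36 |
| Lognormal, median 20 s, log-SD 1.0 | 2.10 | 1.46 |
| Lognormal, median 10 s, log-SD 0.8 | 1.86 | 1.70 |
| Lognormal, median 5 s, log-SD 0.5 | 2.06 | 2.06 |

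In the last row the true mean of 5.7 s is recorded as 11.7 s, an error of 6 s in which the gap plays no part.

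**Do the other planned summaries cure it?** No. The Kaplan-Meier median uses the same reading times. With exponential onsets of mean 1.5 min, the true median of 1.04 min is recorded as 5 min.

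**Comparison with the 60-minute rule.** A recorded mean of 1.0 min with 5% never perceiving becomes 0.95 × 1.0 + 0.05 × 60 = 3.95 min. In Example 2, 2% never perceiving gives 0.98 × 69 + 0.02 × 3600 ≈ 140 s. That adds about 70 s, roughly twice the 36 s grid error.

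**The case against.** The strongest reply is that the matter is small and visible. Onset is secondary and descriptive. The error only makes cooling look slower. The median and mode are reported too. The form shows the grid, so a reader can see that onset is a scheduled reading. An interval-censored analysis cannot recover where in a gap an onset fell. The 60-minute rule may distort the mean more.

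Most of this is correct and limits the point. It does not remove it, because the plan names the mean as the figure to be claimed, and correcting the 60-minute rule would leave the rounding in place.

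Some stronger readings are tempting and do not hold:

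- **That the 1–5 min gap is why every onset is rounded up.** Rounding follows from discrete readings of any spacing. The gap affects only onsets inside it. It is the main cause when medians are about 20 to 30 s with wide spread, and contributes little when nearly all onsets occur within about 10 s.
- **That the claimed onset will be double the truth.** The factor depends on a distribution that the documents do not supply, and it ranges from about 1.2 to 3.
- **That the rule favours the product.** A later onset is conservative for a claim of fast cooling.

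**Conclusion.** The point stands in a limited form. The direction is certain: an onset between readings is recorded late, so the mean that will be claimed is biased late. The size rests on assumed onset distributions. The ratio is about 1.2 to 3 overall. It is typically about 2 when the true mean is roughly 0.5 to 2 min, although narrow lognormals in that region gave from about 1.5 to 3.1. Where onset is nearly immediate, the absolute error is only several seconds.

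A reader might infer that the study's main conclusion is at risk. The documents do not support that: the primary top-2 agreement percentage uses none of these times. The issue is also separate from the 60-minute imputation, which can move the mean more. It merits a correction before analysis because the change is cheap and the figure is intended as a claim.

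**What to change.** In the Synopsis and Section 10.3:

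1. Stop claiming the mean reading time as the onset.
2. Report the cumulative percentage, with 95% CI, who have perceived cooling by each scheduled reading (10 s, 30 s, 1 min, 5 min and so on). Count those who never perceive it as not having perceived. With 400 participants the widest 95% half-width is about 1.96 × √(0.25/400) = 4.9 percentage points.
3. State the median onset as the interval between two readings, or as 'by the X reading'. Treat onset as interval-censored between the last reading without cooling and the first with it, and those who never perceive it as right-censored at 60 min.

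In Example 2 this would report about 24% by 10 s, 66% by 30 s and 86% by 1 min, with the median between 10 and 30 s. The assumed true median is 20 s.

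The cost is wording plus a standard analysis. The visit, form and sample size do not change, and no extra reading is needed. The drawback is that onset becomes an interval or a 'within X' statement and not a single mean, and the data still cannot locate an onset inside a gap.

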## 9.2 Visit Description

### 9.2.1 Screening

#### Pre-Screening Phase

In this study, the test site will recruit participants via an IRB approved screener. Potentially eligible participants will be given an appointment time to visit the site. This process will be 1 to 30 days prior to study start.

#### Screening Phase

**Note: No screening procedures may be performed unless written informed consent has been obtained.** During the screening period, the study staff will screen potential participants to verify they meet the study's eligibility criteria. Not all participants may fulfill the inclusion / exclusion criteria, so a higher number of participants than needed will be asked to participate in the screening examinations. If the (first) screening procedures start on the same day the participant signs the informed consent form/assent (ICF), the time of the participant's signature must be recorded in the participant's file.

After obtaining the participant's signature on the consent form, the below listed screening procedures will be performed and the respective results will be assessed on the day of the first study drug administration:

- allocation of participant identification ([see Section 6.6](#))
- demographic data
- review eligibility
- questioning for special behavior (e.g., eating food or candy, chewing gum, or brushing teeth within one (1) hour prior to enrollment on testing day and not willing to abstain from this at least 1 hour prior to testing)
- participation in previous research studies

No participant will be assigned a participant number unless adherence to all selection criteria as given in Section 6.1 and Section 6.2 is established.

